5.1 Study Time Points

Baseline

The baseline value is defined as the subject's baseline value from the parent study, unless otherwise specified.

First Dose Date of Investigational Product (IP)

For each subject, the first dose date of IP is the date of the first administration of evolocumab in this OLE study.

End of Investigational Product (EOIP) Date

For each subject, end of investigational product is the date reported on End of Investigational Product Administration eCRF.

Last Dose Date of Investigational Product

For each subject, the last dose date of investigational product is defined as the date of the last administration of investigational product (evolocumab or placebo).

If the last dose was administered in-clinic, then the Last IP Dose Date is the last start date captured on the IP Administration (In-Clinic) eCRF page.

If the last dose was administered at a non-investigator site location, then the Last IP Dose Date is defined as the final dose date reported by the subject on the Non-Clinic Final Investigational Product Dose Date eCRF page.

End of Study (EOS) Date

For individual subject, the end of study date is defined as the last day that protocol-specified procedures are conducted for an individual subject, including safety follow-up and survival assessment. The EOS date is recorded on the End of Study eCRF.

Enrollment Date

The enrollment date for each subject is recorded on the Subject Enrollment eCRF **in the OLE study.**

Study Day 1

The date of the first administration of evolocumab in the OLE study or the **enrollment date** for subjects who are not administered any dose of evolocumab.

Study Day

For each subject, and for a given date of interest, study day is defined as the number of days since study day 1:

Study day = (date of interest – study day 1 date) + 1

If the date of interest is prior to the study day 1:

Study day = (date of interest – study day 1 date)

Study End Date

The study end date is the last EOS date of all enrolled subjects.

Endpoint Categories

All time-to-**first**-event endpoints in this study are categorized below.

- Composite
 - time to cardiovascular death, myocardial infarction, hospitalization for unstable angina, stroke, or coronary revascularization, whichever occurs first
 - time to cardiovascular death, myocardial infarction, or stroke, whichever occurs first
 - time to cardiovascular death or hospitalization for worsening heart failure, whichever occurs first

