For analyses based on OLE data only		
Composite or Non-mortality	First event onset date reviewed by CEC in OLE study – enrolment date in OLE study +1	EOS date in OLE study
Mortality	Death endpoint date reviewed by CEC in OLE study – enrolment date in OLE study +1	For subjects who died not due to death endpoint, the censoring date is the death date (reviewed by CEC) in OLE study For remaining subjects, the censoring date is max (EOS date, last known survival status date from eCRF page(s)) in the OLE study

Patient-years of follow-up for treatment emergent adverse events

For analyses based on combined both the parent study and this OLE study:

- 1) Subjects had events: date (first event) – date (first dose date in FOURIER) + 1
- 2) Subjects didn't have events: min [date (EOS in OLE), date (last dose date in OLE)+30] – date (first dose date in FOURIER) + 1

For analyses based on OLE study:

- 1) Subjects had events: date (first event in OLE) – date (first dose date in OLE) + 1
- 2) Subjects didn't have events: min [date (EOS in OLE), date (last dose date in OLE)+30] – date (first dose date in OLE) + 1

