5.3 Other Study Related Definitions

Treatment-Emergent Adverse Event (TEAE)

Events are categorized as Adverse Events (AEs) or **Disease-related Events (DREs)** starting on or after first dose of investigational product as determined by the flag indicating if the event started prior to the first dose on the Events eCRF and up to the EOS/Safety Follow-up visit or 30 days after the last administration of evolocumab, whichever is earlier.

Treatment-Emergent Disease-Related Events

Events categorized as Disease-related Events defined in Protocol Section 9.1.1 starting on or after first dose of investigational product as determined by the flag indicating if the disease-related event started prior to the first dose on the Events eCRF and up to the EOS/Safety Follow-up visit or 30 days after the last administration of evolocumab, whichever is earlier.

Analytical Study Week Assignments

Analytical windows will be used to assign parameters to study weeks. The algorithm is provided in Appendix A.

Investigational Product (IP)

Investigational product includes evolocumab 140 mg every two weeks (Q2W) and 420 mg monthly (QM).

IP Exposure Period in Months (For OLE period)

For subjects whose last IP dose is Q2W:

IP exposure period in OLE period= $[\min(\text{last IP dose date in OLE period} + 14 \text{ days, EOS date}) - \text{first IP dose date in OLE period} + 1] / 365.25 \times 12$

For subjects whose last IP dose is QM:

IP exposure period in OLE period= $[\min(\text{last IP dose date in OLE period} + 28 \text{ days, EOS date}) - \text{first IP dose date in OLE period} + 1] / 365.25 \times 12$

IP Exposure Period in Months (For combined the parent and OLE periods)

For subjects whose last IP dose is Q2W:

IP exposure period in combined periods= $[\min(\text{last IP dose date in OLE period} + 14 \text{ days, EOS date in OLE period}) - \text{first IP dose date in the parent period} + 1] / 365.25 \times 12$

For subjects whose last IP dose is QM:

IP exposure period in combined periods= $[\min(\text{last IP dose date in OLE period} + 28 \text{ days, EOS date in OLE period}) - \text{first IP dose date in the parent period} + 1] / 365.25 \times 12$

Study Exposure Period in Months (For OLE period)

For each subject, study exposure period in OLE period = $[(\text{EOS date} - \text{enrollment date}) + 1] / 365.25 \times 12$

Study Exposure Period in Months (For combined the parent and OLE periods)

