9.5.1 Analyses of Primary Endpoint

The current Medical Dictionary for Regulatory Activities version at the time of data lock will be used to code all adverse events (AEs) and disease related events to a system organ class and a preferred term.

Treatment-emergent adverse events are defined in [Section 5.3](#).

The subject incidence and exposure-adjusted subject incidence rate of all treatment-emergent adverse events, serious adverse events, fatal adverse events, adverse events leading to withdrawal of evolocumab, device-related adverse events, and disease-related events will be tabulated by system organ class (SOC), high level term (HLT), and preferred term (PT) in alphabetical order for the OLE only study period using the OLE safety analysis set. These events will also be presented by yearly subject exposure time intervals. All adverse event summaries for the primary analysis of the primary endpoint will include all treatment-emergent events reported on the Event eCRF, including CEC reviewed events and disease related events.

The analyses described above (subject incidence, exposure-adjusted subject incidence rate) will also be performed combining data from the OLE study and the parent study using the OLE safety analysis set and also be analyzed separately for the subgroup of subjects who were randomized to and received evolocumab group in the parent study with ≥ 7 years of the combined exposure for evolocumab across the **combined** parent and OLE **study**. Events from parent study classified as Target IP TEAEs will be included (adverse events occurring from the first dose of IP date to 30 days after the last dose of IP date or EOS, whichever occurs first). Disease-related events from the OLE study will be reclassified as adverse events and positively reviewed events from the OLE

study will not be included to remain consistent with parent study adverse event reporting. This analysis will be presented by the randomized treatment in the parent study.

Subject incidence of treatment emergent and serious adverse events occurring in at least 1% of the subjects by preferred term will be provided in descending order of frequency for the OLE **only** study period **and combined parent and OLE study periods.**

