9.6.4 Exposure to Investigational Product

Descriptive statistics will be produced to describe the exposure to investigational product for both the OLE **only** study period and combined parent and OLE study periods using the OLE Safety Analysis Set.

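### In the combined FOURIER+OLE tables, former-placebo subjects' event clock and IP exposure start at their first placebo dose, so their column mixes placebo and evolocumab time without saying so

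*SAP*

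**What the plan says.** - **Event clock (SAP 5.1, patient-years for TEAEs).** Under the item "For analyses based on combined both the parent study and this OLE study", the rule for subjects with an event is "Subjects had events: date (first event) – date (first dose date in FOURIER) + 1". For subjects without one it is "min [date (EOS in OLE), date (last dose date in OLE)+30] – date (first dose date in FOURIER) + 1". The same two rules serve both randomized groups.
- **Display (SAP 9.5.1).** FOURIER treatment-emergent events are added to the OLE events, and "This analysis will be presented by the randomized treatment in the parent study".
- **Exposure (SAP 5.3 and 9.6.4).** Combined IP exposure is counted from the "first IP dose date in the parent period", again with no distinction by randomized group. It is tabulated for the "combined parent and OLE study periods using the OLE Safety Analysis Set".
- **Meaning of IP.** SAP 5.3 states "Investigational product includes evolocumab 140 mg every two weeks (Q2W) and 420 mg" monthly, and does not mention placebo. SAP 5.1 takes a wider view: "the last dose date of investigational product is defined as the date of the last administration of investigational product (evolocumab or placebo").
- **Treatment in the OLE (Protocol 5.1).** Everyone receives evolocumab. Because the analysis set is limited to OLE-dosed subjects (SAP 6.1 and 10), every subject in the placebo column crossed over.

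No section splits that column at the switch or labels it as placebo followed by evolocumab.

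**The concern.** The study's aim is to describe the long-term safety of evolocumab, and long total exposure is part of its stated rationale (Protocol 2.3). In the combined table the former-placebo column is neither a placebo rate nor an evolocumab rate. The clock stops at the first event, so a subject whose first event of a given type fell on placebo contributes no evolocumab time, and no evolocumab event, to that row. For uncommon events the column is mostly evolocumab time; for very common ones it is mostly placebo time. One general footnote cannot tell the reader what each row measures.

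The exposure table has a related defect. Under the SAP 5.3 meaning of IP, a former-placebo subject has no parent-period start date. Under the SAP 5.1 meaning the formula works, but placebo years appear as IP exposure in a report whose subject is evolocumab exposure.

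**Working it through.** **The plan's own figure.** Protocol 2.3 expects about 1000 subjects with 7 years on evolocumab: 2000 × 0.50 = 1000, and 2 + 260/52 = 7 years. Both reproduce.

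**Exposure.** The OLE lasts 260 × 7 / 365.25 = 4.98 years. A former-placebo subject with 2 years in FOURIER who completes the OLE gets 2 + 4.98 = 6.98 years of combined IP exposure under SAP 5.3.

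- Evolocumab share: 4.98 / 6.98 = 71%. Placebo share: 29%.
- With 1 year in FOURIER the evolocumab share is 83%; with 3 years it is 62%.
- If placebo counts as IP, about 2000 of the subjects with at least 2 years in FOURIER could show about 7 years, against the 1000 in Protocol 2.3 who would have them on evolocumab.

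**Event rates.** The documents give no event rates, so those below are assumptions. The model has a constant placebo hazard a for f years, then a constant evolocumab hazard b for g years, with no dropout. Following the SAP 5.1 clock:

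- P(event) = 1 − exp(−af − bg)
- Expected time = (1 − exp(−af))/a + exp(−af) × (1 − exp(−bg))/b
- Column rate = P(event) / expected time. The evolocumab column has rate b.

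With f = 2, g = 5, a = 0.02 and b = 0.04 per year (true ratio 2.0):

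- P = 1 − exp(−0.24) = 0.2134
- Time = 1.961 + 4.354 = 6.315 years
- Column rate = 0.0338; apparent ratio = 0.04 / 0.0338 = 1.18

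With a = 0.02 and b = 0.03 (true ratio 1.5):

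- P = 1 − exp(−0.19) = 0.1730
- Time = 1.961 + 4.461 = 6.422 years
- Column rate = 0.0269; apparent ratio = 1.11

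At lower rates, 0.5 against 1.0 per 100 patient-years, a true ratio of 2.0 reads 1.17.

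Apparent ratio when the true ratio is 1.5, with g = 4.98:

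| Placebo rate per 100 patient-years | 1 year in FOURIER | 2 years | 3 years | Evolocumab share of the column's time (2 years) |
|---|---|---|---|---|
| 0.5 | 1.06 | 1.11 | 1.15 | 71% |
| 5 | 1.07 | 1.13 | 1.17 | 66% |
| 30 | 1.14 | 1.24 | 1.31 | 42% |
| 80 | 1.28 | 1.40 | 1.46 | 14% |

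The effect also runs the other way: at 0.5 per 100 patient-years and 2 years in FOURIER, a true ratio of 0.8 reads 0.93.

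**Equal rates.** If a = b the column rate equals the common rate and nothing is distorted. The mix still varies. At 50 per 100 patient-years in both periods, with 2 + 5 years, 1 − exp(−1) = 63% of subjects have their first event on placebo. Placebo then makes up [0.632/0.5] / [(1 − exp(−3.5))/0.5] = 1.264 / 1.940 = 65% of the column's time at risk.

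**The case against.** The best defence is that this analysis is supplementary and descriptive. SAP 9.1 plans no inference, the SAP specifies no ratio between columns, and it nowhere calls the placebo column a control. Columns by randomized group can properly be read as early against delayed start, and they apply the same selection (survival and staying on IP through FOURIER) to both arms. All of this stands. It makes the fault one of definition and labelling rather than an invalid test, and it is a reason to keep the display. But the SAP does not state the early-versus-delayed reading.

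Clean views also exist. The OLE-only analysis, which the protocol makes primary (10.4.1), restarts everyone's clock at the first OLE dose. The separately analysed subgroup randomized to evolocumab with at least 7 years of exposure is free of the blend. However, the first omits the FOURIER evolocumab years, and the second is selected on long exposure, so subjects who died or stopped sooner are not in it.

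A reader might infer that the remedy is to set enrollees' FOURIER placebo time beside all evolocumab time. The eligibility rules do not support that. Subjects had to complete FOURIER still on assigned product (Protocol 4.1.1, criterion 102), and permanent discontinuation excluded them (4.1.2, criterion 201). Fatal events and events leading to permanent withdrawal would be essentially zero in that placebo period by design, which would create an artificial evolocumab excess.

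A reader might also infer that an overall column adds the placebo years to total exposure. SAP 9.1 asks for an overall summary of endpoints unless otherwise specified. SAP 9.5.1 specifies randomized treatment for the combined event table, and 9.6.4 names no columns. The documents do not clearly plan that column for these tables.

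**Conclusion.** The concern holds for the combined FOURIER+OLE event and exposure tables only. Former-placebo subjects' patient-years and IP exposure run unbroken from the first placebo dose, and the SAP gives two meanings of IP. For a subject with 2 years in FOURIER, about 2 of about 7 years of combined IP exposure are placebo.

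If rates differ by treatment, the contrast between the columns is attenuated. With 2 + 5 years, a true 1.5 reads about 1.11 and a true 2.0 about 1.18 for uncommon events, with less attenuation for very common ones. These figures rest on assumed constant hazards and no dropout. The 2-year duration is a planning figure for about 2000 of the 5000 subjects, hence the range over 1 to 3 years. If rates are equal, the column rate is right and only its description is wrong.

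It would go too far to conclude that the primary safety results are biased: the OLE-only clock is evolocumab time in both columns. The evolocumab-randomized column is also essentially evolocumab throughout, apart from the gap between studies. That gap should be at most 90 days (Protocol 7.2), about 3% of a 2 + 5 year clock.

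**What to change.** 1. Reconcile the meaning of IP in SAP 5.1 and 5.3. Define combined evolocumab exposure from the first evolocumab dose: the first FOURIER dose for subjects randomized to evolocumab, the first OLE dose for those randomized to placebo. Report this in 9.6.4.
2. In 5.1 and 9.5.1, add an all-evolocumab-exposed summary of combined TEAE incidence and exposure-adjusted rates, with the first-event clock restarting at that dose.
3. Keep the randomized-group display, and label the columns *placebo then evolocumab* and *evolocumab throughout*, to be read as delayed against early start.
4. Do not present enrollees' FOURIER placebo time as a comparator column.

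The cost is SAP wording and reprogramming of supplementary tables. The dates needed are already held, and no new data are required.

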9.5.2 Analyses of Secondary Endpoints

Summary statistics of the secondary endpoints (percent change of LDL-C from baseline and achieving an LDL-C level < 40 mg/dL) will be analyzed based on the OLE Safety Analysis Set at each scheduled visit **for the combined parent and OLE study periods.**

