This study (FOURIER OLE) requires laboratory assessments at week 12 and thereafter approximately every 24 weeks from day 1; the corresponding blood samples will be processed using a central laboratory. To preserve the integrity of FOURIER blinding, no local lipid assessments may be performed until either FOURIER is unblinded or at least 12 weeks after a subject's last administration of FOURIER investigational product (evolocumab or placebo), whichever is first.

Upon enrollment in this study (FOURIER OLE), subjects will receive evolocumab 140 mg every 2 weeks (Q2W) or 420 mg monthly (QM), according to the subject's preference. The frequency and corresponding dose of administration can be changed at any scheduled time point where evolocumab is supplied to the subject, provided the appropriate supply is available. It is recommended that subjects continue the same background lipid-lowering therapy (LLT), including statin, as taken during FOURIER.

This study will continue for 260 weeks (approximately 5 years). Subjects ending administration of evolocumab should continue study assessments until the end of study.

Approved

All subjects will be followed and complete procedures/assessments from enrollment through the date of study termination unless the subject has withdrawn consent, irrespective of whether the subject is continuing to receive treatment. All deaths and cardiovascular events of interest will be reviewed by an independent external Clinical Events Committee (CEC), using standardized definitions.

Sample Size: Approximately 5000 subjects will be enrolled, including approximately 2000 subjects with ≥ 2 years of study exposure in FOURIER.

Summary of Subject Eligibility Criteria: Subjects must have completed FOURIER (Study 20110118) while still receiving assigned investigational product and provided informed consent for this OLE study. Eligible subjects may not be currently receiving treatment in another investigational device or drug study, or have ended treatment on another investigational device or drug study(ies) within less than 4 weeks. Women cannot be pregnant or breastfeeding or planning to become pregnant or planning to breastfeed during treatment with evolocumab and within 15 weeks after the end of treatment with evolocumab. Women of childbearing potential must be willing to use an acceptable method(s) of effective birth control during treatment with evolocumab and for an additional 15 weeks after the end of treatment with evolocumab.

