1.2 Secondary

The secondary objectives are the following:

- to describe the effects of long-term administration of evolocumab on low-density lipoprotein cholesterol (LDL-C) levels
- to describe the effects of long-term administration of evolocumab in subjects achieving an LDL-C level < 40 mg/dL (1.03 mmol/L)

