Appendix D. Recommended Lipid-lowering Background Therapy

It is recommended that subjects continue the same background LLT, including statin, as taken during FOURIER. Background LLT should be optimized for the individual subject consistent with local professional society guidelines. All subjects should receive at least an effective statin dose, ie, at least atorvastatin 20 mg daily or equivalent. Where locally approved, highly effective statin therapy, defined as at least atorvastatin 40 mg daily or equivalent, is recommended.

No other lipid therapy is required for the FOURIER OLE study. Ezetimibe and other commercially available lipid therapy at dosages approved by local regulatory authorities may be added to any of these regimens except excluded medication as per [Section 6.8](#). These therapies, including statins, are not provided or reimbursed by Amgen (except if required by local regulation). Background LLT received at enrollment should remain unchanged throughout the entire duration of the study.

Approved

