6.1 OLE Safety Analysis Set

The OLE safety analysis set includes all subjects who received at least 1 dose of open-label evolocumab in the OLE study. **There may be sites which enrolled subjects and closed due to COVID, and those sites may have issues providing source documentation for clinical trial data verification. We will exclude the subjects from those sites for all analysis sets if their data are not able to be verified successfully via the full source documentation verification process. Since only a minimal number of subjects' data are excluded compared with the number of subjects enrolled in this study, no sensitivity analyses will be performed.**

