8.3 Handling of Missing and Incomplete Data

8.3.1 Patterns of Missing Data

Subjects may be missing specific data points for various reasons. In general, data may be missing due to a subject's early withdrawal from study, a missed visit, or non-evaluability of a data point or an endpoint at a particular point in time. All attempts will be made to capture missing or partial data for this trial prior to the data cutoff date.

The frequency and pattern of missing data for selected endpoints will be assessed through descriptive summaries of the measurements over time.

There will be no imputation for missing data other than date imputation described in the next section.

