Appendix A. Analytical Study Week Assignments

Selected endpoints will be summarized by scheduled study visits in descriptive analyses. Since the actual visits may not exactly coincide with their scheduled visit day, the actual visit day is mapped to the study visit generally by non-overlapping consecutive intervals covering the entire time continuum. The mapping intervals for all distinct schedules are summarized in the following table.

If there is more than one record in a given analytical window, the analytical record for that scheduled visit will be defined as the record closest to the scheduled visit day (7 days x Number of Study Weeks + 1) for that scheduled visit. If two records are equidistant from the scheduled visit day, then the earlier record will be chosen. If there are multiple records on the same day, the last record will be used.

[figure not shown]
Analytical Study Week	Scheduled Visit Day	Laboratory (lipid panel, ApoA1, ApoB, Lp(a), and serum pregnancy)	Vital signs			
			Body weight	Concomitant therapy	Physical exam	CANTAB assessment
Week 12	85	(1, 126]		(1, 126]		
Week 24	169	(126, 252]		(126, 252]		
Week 48	337	(252, 420]		(252, 420]		(1, 504]
Week 72	505	(420, 588]		(420, 588]		
Week 96	673	(588, 756]		(588, 756]		(504, 840]
Week 120	841	(756, 924]		(756, 924]		
Week 144	1009	(924, 1092]		(924, 1092]		(840, 1176]
Week 168	1177	(1092, 1260]		(1092, 1260]		
Week 192	1345	(1260, 1428]		(1260, 1428]		(1176, 1582]
Week 216	1513	(1428, 1666]		(1428, 1595]		
Week 240	1681			(1596, 1750]		
Week 260	1821	(1666, EOS]		(1750, 1836]	> 1	(1582, EOS]

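### The LDL-C visit summaries mix values drawn on and off evolocumab, so an unchanged on-drug effect could look like waning

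*SAP*

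**What the plan says.** The first secondary objective (Protocol 1.2) is "to describe the effects of long-term administration of evolocumab on low-density lipoprotein cholesterol (LDL-C) levels". Observation does not end with treatment: "Subjects ending administration of evolocumab should continue study assessments until the end of study" (Protocol synopsis; 3.1 and 6.2.2 agree), and Protocol Table 1 schedules fasting lipids through week 260.

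On the analysis side:

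- SAP 6.1: "The OLE safety analysis set includes all subjects who received at least 1 dose of open-label evolocumab in the OLE study". Apart from dropping sites whose data cannot be verified, nothing else limits membership.
- SAP 9.5.2: percent change in LDL-C and "achieving an LDL-C level < 40 mg/dL) will be analyzed based on the OLE Safety Analysis Set at each scheduled visit", over the combined parent and OLE periods. It contains no on-treatment restriction.
- SAP Appendix A maps measurements by study day alone, to "non-overlapping consecutive intervals covering the entire time continuum". The last lipid window runs from day 1666 to EOS.
- SAP 8.3.1: "There will be no imputation for missing data other than date imputation described in the next section".
- SAP 5.3, by contrast, ends treatment-emergent adverse events at the EOS/safety follow-up visit or "30 days after the last administration of evolocumab, whichever is earlier". Lipids have no matching rule.

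On background therapy, Protocol Appendix D says "Ezetimibe and other commercially available lipid therapy at dosages approved by local regulatory authorities may be added to any of these regimens". The same appendix closes by asking that the regimen at enrollment stay the same for the whole study.

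**The concern.** The objective is about LDL-C under administration of evolocumab. The planned table describes LDL-C in everyone who once received it in the OLE, whatever they were taking when the sample was drawn. The two coincide only while nearly all sampled subjects are still on drug.

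Over 260 weeks the off-drug share may rise. A mean that drifts toward zero, or a falling share below 40 mg/dL, could then come from a weakening effect or from people stopping. The planned outputs cannot tell these apart, and the OLE has no concurrent control arm to help. Discontinuation of product (SAP 9.2), exposure (SAP 9.6.4) and changes in lipid medication (SAP 9.6.5) are each tabulated, but none is linked to LDL-C. The subgroup with at least 7 years of combined exposure (SAP 4.2) is named in SAP 9.5.1 for adverse events and is not mentioned in 9.5.2.

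At stake is the interpretation of both secondary endpoints. The primary safety endpoint is unaffected.

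**Working it through.** **The plan's own figure.** The only sizing figure is the table of 95% confidence interval widths for adverse event rates at N = 5000. It reproduces: for 5%, 2 × 1.96 × √(0.05 × 0.95 / 5000) = 1.208%. It has no bearing on LDL-C. The documents give no LDL-C precision and no discontinuation rate, so what follows is illustration.

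**Inputs.**
- On-drug fall R: 55% to 75% (Protocol 2.1; this is versus placebo, used here as a stand-in for change from baseline).
- Effect of a nonstatin add-on: 15% to 20% (Protocol 2.1).
- Share q of *observed* values drawn off drug: assumed 5% to 30%.
- Off-drug LDL-C: assumed back at baseline, then relaxed.

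**1. Mean percent change.** With full return to baseline, visit mean = −(1 − q) × R.

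| q | R = 55% | R = 75% |
|---|---|---|
| 5% | −52.3% | −71.3% |
| 10% | −49.5% | −67.5% |
| 20% | −44.0% | −60.0% |
| 30% | −38.5% | −52.5% |

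Each 10% of values drawn off drug costs 0.10 × R, which is 5.5 to 7.5 percentage points.

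**2. Share below 40 mg/dL.** Assume 70% on drug and none off drug. The visit share is 0.70 × (1 − q): 63%, 56% and 49% at q = 10%, 20% and 30%. If 2% of off-drug values are below 40 mg/dL, these become 63.2%, 56.4% and 49.6%.

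**3. Incomplete return.** If off-drug values sit at −10% rather than 0, then at q = 20% and R = 55% the mean is −(0.8 × 55 + 0.2 × 10) = −46.0%, not −44.0%. If every off-drug subject took an add-on worth 15% to 20%, it would be −47% to −48%.

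**4. Attendance.** Nothing is imputed, so a subject who stops and also misses visits adds no value. Let d be the share of subjects off drug. Assume attendance of 95% on drug and a off drug. Then q = d × a / [d × a + (1 − d) × 0.95].

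| d | q at a = 25% | q at a = 50% | Mean when R = 55% |
|---|---|---|---|
| 10% | 2.8% | 5.5% | −53.4% to −52.0% |
| 20% | 6.2% | 11.6% | −51.6% to −48.6% |
| 30% | 10.1% | 18.4% | −49.4% to −44.9% |

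Dilution depends on q, not d, and can be well below what the share of subjects off drug suggests.

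**5. Added therapy in subjects still on evolocumab.** Suppose 20% of them take an add-on worth 15% to 20%. Their fall is 1 − 0.45 × 0.85 = 61.75% to 1 − 0.45 × 0.80 = 64%. The mean moves from −55% to −(0.8 × 55 + 0.2 × 61.75) = −56.4%, or to −(0.8 × 55 + 0.2 × 64) = −56.8%. That is under 2 points. Reduced background therapy would move it the other way.

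**The case against.** The strongest reply is that this is a single-arm descriptive study without inference (Protocol 10.4.1, SAP 9.1), and that a summary of all observed values is a legitimate description. No section claims durability under continued dosing or states an estimand. Medians and quartiles are also planned (SAP 9.1) and are less sensitive than the mean: with assumed SDs of 15 to 25 points on drug and 25 off drug, the median at q = 10%, 20% and 30% is about −52%, −49% and −45%, against means of −49.5%, −44.0% and −38.5%. Readers will also have the tables of discontinuation, exposure and therapy changes.

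Much of this stands. The all-values table should stay, and the median softens the effect. But the SAP never says that the table follows a treatment-policy approach, and separate marginal tables cannot show what share of the values at a given visit was drawn off drug. Sensitivity analyses for bias are only conditional (SAP 8.4).

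An on-treatment table is not neutral either. Its members are selected for staying on drug. Stopping at the first background-therapy change could remove subjects whose LDL-C prompted that change. A bare 14- or 28-day limit would also drop compliant samples: if the last QM dose falls at week 256, a week 260 draw at the end of its +14-day window comes 28 + 14 = 42 days after dosing.

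**Conclusion.** The gap is real. Off-drug LDL-C values enter both secondary summaries, and no output identifies them. They enter by omission, through an all-treated set, windows running to EOS and no exclusion rule; the SAP does not say so outright. If their share of observed values rises, an unchanged on-drug effect could look like waning. The illustrative size is 5.5 to 7.5 percentage points in the mean per 10% of observed values drawn off drug. This assumes an on-drug fall of 55% to 75% and full return to baseline, and it shrinks with lower off-drug attendance or other lipid therapy.

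A reader might infer more than this, in three ways that the documents do not support:

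- That discontinuation *will* read as loss of effect, by a known amount. No discontinuation rate is given, and only observed values count, so only the direction can be stated.
- That added lipid therapy props up the late means. Background changes can move LDL-C either way, and the illustrated shift is small. Appendix D both permits additions and asks for no change; those statements must be reconciled.
- That durability should be read from an on-treatment table alone. That table carries its own selection.

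**What to change.** In SAP 9.5.2:

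1. Label the planned all-values table as treatment-policy, and keep it.
2. Add a supplementary on-treatment summary of both secondary endpoints at each OLE visit, showing the number on drug.
3. Count a value as on-treatment if it was drawn within the dosing interval after the last dose (14 days for Q2W, 28 days for QM, the intervals already used for exposure in SAP 5.3) plus the 14-day visit window of Protocol Table 1. That is 14 + 14 = 28 days for Q2W and 28 + 14 = 42 days for QM.
4. State how temporary interruptions are handled, since a last-dose date does not capture them. For home dosing, Protocol 6.2.1 requires as a minimum only dispensing and return records, so the rule should say which records it uses.
5. Interpret the two tables together. A further version that stops at the first background-therapy change is optional.

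The cost is one more table, built from last-dose dates already defined in SAP 5.1; the optional version would use therapy dates recorded under Protocol 6.3.1. The downside is that the on-treatment group is selected for persistence, which a footnote should state.
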